2.0 Clinical study

The trial will be conducted in compliance with the protocol, GCP and the applicable regulatory requirement(s).

Trial Objectives and Purpose

The main objectives of the research study is to evaluate the safety, efficacy and costeffectiveness of a bio-inspired artificial pancreas (BiAP) with, and without, the addition of an adaptive bolus calculator (ABC4D) compared to gold-standard sensor-augmented pump therapy.

Hypothesis

- 1. A bio-inspired artificial pancreas (BiAP) device has a positive impact on glucose control, as measured by time in target after 6 weeks of use, when compared with sensor-augmented pump with low-glucose suspend (LGS).
- 2. A bio-inspired artificial pancreas (BiAP) device with an adaptive bolus controller (ABC4D) has an additional positive impact on post-prandial glucose control.

Trial Design

A 3-way crossover randomized controlled trial (Fig 3). Description of the three arms:

- 1. Sensor augmented pump (open-loop)
- 2. BiAP with a fixed bolus calculator
- 3. BiAP with the Advanced Bolus Calculator for Diabetes (ABC4D)

The primary outcome from the studies will be % time spent with a glucose concentration in the target range (3.9-10.0mmol/l). This outcome incorporates safety as it ensures participants do not have low or high glucose excursions and is the principal measure of efficacy for closed-loop insulin delivery systems in the scientific literature. Other measured outcomes will be % time spent in euglycaemia (3.9-7.8mmol/l), % time spent in hypoglycaemia (<3.9mmol/l), % time spent in hyperglycaemia (>10mmol/l), mean venous blood and sensor glucose, glycaemic variability as measured by standard metrics (SD, CONGA, LI, JINDEX, GRADE, MODD, MAGE, ADDR, MVALUE, MAG), glycaemic risk as measured by low blood glucose index (LBGI) and high blood glucose index (HBGI), closed-loop error grid analysis, glucose area under the curve. All measures have been previously published and validated. Quality of life, treatment satisfaction and device acceptability outcomes will be measured using mixed methods (questionnaires and semi-structured interviews).

Methodology Randomised controlled cross-over open label study

Timescale It is anticipated that the study will take 1 year, each subject will be in the study for up 6 months, with a total of 6 visits in that timeframe.

Population

n = 20

Inclusion criteria

- Adults over 18 years of age
- Type 1 diabetes confirmed on the basis of clinical features and a random c-peptide <200 pmol/L
- Type 1 diabetes for greater than 1 year
- Continuous subcutaneous insulin infusion for greater than 6 months
- Structured education done (either 1:1 or group education)
- HbA1c <10% (86mmol/mol)
- A negative pregnancy test in female participants of childbearing age

Exclusion criteria

- More than one episode of severe hypoglycaemia (defined as hypoglycaemia requiring 3rd party assistance) in the preceding year
- Impaired awareness of hypoglycaemia (Gold score >4)
- Pregnant or planning pregnancy
- Breastfeeding
- Enrolled in other clinical trials
- Have active malignancy or under investigation for malignancy
- Severe visual impairment
- Reduced manual dexterity
- Ischaemic heart disease
- Anti-anginal medications (e.g. GTN)
- Regular use of paracetamol
- Unable to participate due to other factors, as assessed by the CI

Subject withdrawal criteria

Participants will be withdrawn from the study in the case of:

- 1. Loss of capacity to give informed consent
- 2. Cessation of CSII as usual care for type 1 diabetes

- 3. Recurrent (>1 episode) severe hypoglycaemia (defined as needing 3rd party assistance)
- 4. Terminal illness

Withdrawal will be immediate and participants will be followed up in the appropriate outpatient diabetes clinic within 4 weeks of withdrawal.

Recruiting will be undertaken in the insulin pump clinics at Imperial College Healthcare NHS Trust, from registered research databases and from interested participants who contact us. Participant information sheets will be given to potential participants and, after a minimum of 48 hours and following any questions, informed consent will be taken.

Usual care will be maintained for diabetes throughout the study. No concomitant medical therapies are contra-indicated, except for GLP-1 analogues and high dose steroids.

[figure not shown]

Fig.3 Study design.

CSII – Continuous Subcutaneous Insulin Infusion, SAP – Sensor Augmented Pump, CGM – Continuous Glucose Monitoring, BiAP – Bio-inspired Artificial Pancreas, ABC4D – Advanced Bolus Calculator for Diabetes

Visit 1: Screening

- Routine clinical examination
- ECG
- Venous blood taken for glucose, c-peptide, HbA1c, lipids, creatinine

- Urine pregnancy test in female participants of childbearing age
- Random urine sample for albumin: creatinine ratio (UACR) ratio and c-peptide creatinine ratio (UCPCR)
- Gold score
- Continuous glucose monitoring (Dexcom) will be connected according to manufacturer's instructions. Participants will be shown how to insert the sensor themselves and written instructions on how to calibrate the CGM every 12 hours and sensor change every 7 days as per manufacturer's instructions will be provided. Participants will be asked to wear the CGM for 2 weeks in total.
- Participants will be provided with the study pump and receive training on how to use it.
- Mixed methods psychological assessment: Diabetes quality of life (DQOL), Diabetes Treatment Satisfaction Questionnaire (DTSQ) and PAID Questionnaire to be completed. Semi-structured interviews by the investigators will be carried out.

Visit 2: CGM review

- 14 days following visit 1
- Remove CGM, upload data and review results with the participant.
- Make adjustments to insulin: carbohydrate ratio(ICR), insulin sensitivity factor (ISF), insulin basal infusion rates if necessary.

Randomisation:

The order of the three intervention arms will be completely randomised using sealed envelope (www.sealedenvelope.com).

Irrespective of which intervention the participants are allocated to for the first 6 weeks they will spend the first 24 hours at the clinical research facility for education and training on how to use the BiAP system as a whole (as outlined under visit 3).

Visit 3: 24 hours in clinic and start of 1st 6-week intervention period

- Attend the CRF at 16:00 until next day at 18:00.
- Participant will be connected to the BiAP system at 17:00.
- Finger prick blood sampling will be done eight times (before after each meal, bettime, one random during night) and analyzed immediately for glucose concentration using a standard glucometer.

- Standardized meals will be provided at 19:00 (dinner), 07:00 (breakfast) and 12:00 (lunch).
- The research team will ensure that the participants are comfortable with the BiAP system, particularly in the following situations:
- > How to switch the system from open-loop to closed-loop and vice versa.
- > When to calibrate the CGM system.
- When to seek help.
- Should the participant want a snack overnight they can record the carbs on the smartphone. For snacks of 15g or below participants will be advised not to bolus, but in cases of larger snacks they can calculate the bolus using the meal announcement button on BiAP/smartphone. Participants will be shown how to do this.
- They will be free to go home at 18:00 with the BiAP device to continue the remaining 6 weeks.
- Participants will be trained to use the sensor, controller and insulin pump.
- They will have a structured education refresher.
- All training will be delivered by the study team and will be supported with written information. Participants will be expected to be able to self-manage the sensor, controller and pump prior to leaving the clinical research facility and competencies will be clearly recorded. Videos to support sensor insertion, and pump cannula and reservoir operations will be provided to all participants via email or on a USB stick and can be uploaded to participants' smartphones for off-line use. Contact details for clinical and technical support will be provided.
- The study team will phone the participants on day 1, day 3, day 7 and at 3 weeks.

Visit 4: End of first 6-week intervention period

- Attend the clinical research facility.
- Review any issues with the technology used.
- Download data from the study pump (the pump stores data for 90 days).
- Provide consumables (sensors, transmitter, insulin infusion sets) for the next 6-week intervention period.
- Gold score
- Mixed methods psychological assessment: Diabetes quality of life (DQOL), Diabetes Treatment Satisfaction Questionnaire (DTSQ) and PAID Questionnaire to be completed. Semi-structured interviews by the investigators will be carried out.
- Acceptability questionnaire to be completed.
- Repeat urine pregnancy test in female participants of childbearing age

• Participants will be instructed to revert back to their usual care for 2 weeks (wash-out period) before commencing the next intervention for 6 weeks.

Visit 5: End of 2nd 6-week intervention period

- Attend the clinical research facility.
- Review any issues with the technology used.
- Download data from the study pump.
- Provide consumables (sensors, transmitter, insulin infusion sets) for the next 6-week intervention period.
- Gold score
- Mixed methods psychological assessment: Diabetes quality of life (DQOL), Diabetes Treatment Satisfaction Questionnaire (DTSQ) and PAID Questionnaire to be completed. Semi-structured interviews by the investigators will be carried out.
- Acceptability questionnaire to be completed.
- Repeat urine pregnancy test in female participants of childbearing age
- Participants will be instructed to revert back to their usual care for 2 weeks (wash-out period) before commencing the next intervention for 6 weeks.

Visit 6: End of 3rd 6-week intervention period and end of study

- Attend the clinical research facility.
- Review any issues with the technology used.
- Gold score
- Mixed methods psychological assessment: Diabetes quality of life (DQOL), Diabetes Treatment Satisfaction Questionnaire (DTSQ) and PAID Questionnaire to be completed. Semi-structured interviews by the investigators will be carried out.
- Acceptability questionnaire to be completed.
- Participants will be asked to return all components of the study device and will be instructed to revert back to their usual care.

Activity / Visit no	1	2	3	4	5	6	Additional information
Insertion of CGM sensor	X						Participants will change the sensor every week at home throughout the study
CGM review with participant		х					
Randomisation + Initialise the			Х	Х	Х		

Table: Overview of activities at each visit for participants

intervention/control							
Update CBR algorithm with new							This will be done automatically in
cases							the BiAP+ABC4D intervention
Clinical examination	x						
Weight measurement	x						
Venous blood test	Х						
Urine test	Х			Х	Х		
Pregnancy test (if applicable)	Х						
ECG	Х						
Questionnaire/s	Х			Х	Х	Х	
Follow-up clinical visits		Х	Х	Х	Х	Х	
Overnight stay in clinical			х				
research facility							
Semi-structured interview	Х			х	х	х	

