It is well-known that insulin requirements change during pregnancy and hence participants who are female and of childbearing age will have a urine pregnancy test done at screening and prior to each intervention. Participants will be excluded from the study if they are pregnant or planning pregnancy within the study time frame, to minimise any potential risk.

It is acknowledged that the clinical schedule is demanding of subject's time and includes overnight visits. This inconvenience is necessary to adequately and safely ensure participants receive the appropriate training on how to use the device and we will minimise the burden as much as possible by providing entertainment (TV, radio, reading material, internet access) in a comfortable environment with privacy. We will also ensure to make every effort to schedule visits around participants' lifestyles.

Research participants will benefit from being in the study by having increased access to diabetes professionals and more frequent visits to hospital with an emphasis on improved glycaemic control. They will also have the opportunity to use continuous glucose monitoring and review the results with a consultant diabetologist experienced with monitoring. The benefits to people with T1DM include the potential to carry forward technology to improve the risks of high glucose concentration leading to complications and distressing low glucose values.

Route of administration, dosage, dosage regimen, and treatment period

Insulin will be administered subcutaneously or intraperitoneally (in those who already have IP access with a DiaPort). This is the standard route of administration for insulin in T1DM. Alternative routes of administration include intravenous or inhaled. Intravenous insulin is used clinically in people with diabetes who are acutely unwell or those unable to eat and drink, inhaled insulin is no longer commercially available in the UK. The insulin dosage will be expressed as units infused subcutaneously as microboluses and will be calculated by the control algorithm of the closed-loop at 5-minute intervals. The treatment periods are defined by time spent in closed-loop insulin delivery.

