3.0 Statistics

From our previous published data^{1,6} we anticipate that the BiAP/ABC4D intervention will increase the percentage of time for which plasma glucose concentrations were in the target range by a mean of 6% (SD 9.9) compared with the BiAP/fixed bolus artificial pancreas system, and by an estimated mean of more than 6% (9.9) compared with the control group. We intend to do three pairwise comparisons between the interventions, and therefore have conducted a power analysis using the typical sample size formula for the paired t test. We estimate, using mean 12% (9.9), that 20 participants would provide 90% power at the 5% significance level (corrected for multiple comparisons) to detect differences between the three interventions.

Missing, unused, and spurious data will be assessed on an individual basis and may be ignored, withdrawn or the visit may be removed from the analysis with appropriate justification adjudicated by the Principal Investigator.

Efficacy

Primary outcome will be:

• % time in target range defined as 3.9-10mmol/l

Secondary outcomes will be:

- % time spent in euglycaemia (3.9-7.8mmol/l)
- % time spent in hypoglycaemia (<3.9mmol/l)
- % time spent in hypoglycaemia (<2.8mmol/l)

- % time spent in hyperglycaemia (>10mmol/l)
- % time spent in severe hyperglycaemia (<15mmol/l)
- Mean sensor glucose
- Glycaemic variability
- Glycaemic risk as measured by LBGI and HBGI
- Closed loop error grid analysis
- Glucose area under the curve
- Insulin requirement in units/kg/hr
- Hypoglycaemia awareness (Gold scores)
- Quality of life by mixed quantitative and qualitative methodologies
- Cost-effectiveness
- Device usability and acceptability
- % time in closed loop control
- Severe hypoglycaemia
- Diabetic ketoacidosis
- Sensor MAD%

These are validated, published metrics, which will be assessed at the end of each visit from CGM data. There will be an interim analysis of the data after each visit to ensure efficacy and safety.

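### The primary outcome has no stated CGM window or denominator, and the protocol's only definition of a treatment period cannot apply to the open-loop control arm

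*Combined protocol and SAP*

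**What the plan says.** The primary outcome is stated twice, under Trial Design in section 2.0 and under Efficacy in section 3.0. The second statement is % "time in target range defined as 3.9-10mmol/l". Both give the glucose range. Neither gives the stretch of CGM data, the denominator or a minimum amount of data.

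Four other places bear on timing:

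- Section 2.0, Hypothesis 1: the effect is judged "as measured by time in target after 6 weeks of use".
- Section 3.0, after the list of secondary outcomes: the metrics are ones "which will be assessed at the end of each visit from CGM data".
- Section 2.0, visit schedule: every arm has 6-week intervention periods, as in "Visit 4: End of first 6-week intervention period".
- Section 1.0, Route of administration, dosage, dosage regimen, and treatment period: "The treatment periods are defined by time spent in closed-loop insulin delivery".

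The first of the three arms is listed as "Sensor augmented pump (open-loop". Section 3.0 also has % "time in closed loop control" as a secondary outcome. Under Visit 3, all participants attend the clinic for BiAP training whatever their allocation, and are connected to the system from 17:00 until they leave at 18:00 the next day.

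**The concern.** An analyst who looks for the period over which to compute time in range finds one explicit definition, and it is tied to loop status. Time with the loop off is foreseen in the BiAP arms. The Safety text in section 1.0 describes reversion to a basal rate after a controller failure, and Visit 3 trains participants to switch between open and closed loop. Dropping those hours would select data after randomisation, on a variable that only the BiAP arms have. The within-person comparison with control would then no longer be like with like.

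The setting adds to the risk. The trial is open label, section 3.0 plans an interim analysis after each visit, and missing, unused or spurious data are handled case by case. A window not fixed in advance could be settled after results are known.

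There is also a smaller problem at the other end. The Visit 3 stay opens period 1, so participants allocated to control first spend about a day connected to BiAP inside a control period. Nothing says whether those hours count.

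**Working it through.** **The plan's own figure.** The only number tied to the primary outcome is the sample size: 20 participants, 90% power, mean difference 12 points (SD 9.9), 5% level corrected for three comparisons. Take a paired t test with 9.9 as the SD of the difference and two-sided alpha 0.05/3 = 0.0167 (Bonferroni is my assumption; no method is named). Then 13 participants are enough, and 20 give 99.5% power. If 9.9 is instead a per-treatment SD with no within-person correlation, N is 19 (normal approximation) or 22 (exact t). The stated 20 is therefore not reproduced exactly, but that is a separate matter. No input to it depends on the window, and I use the 12 points only as a yardstick.

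**The treatment-period sentence against the rest of the protocol.**

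- Control arm: it is open loop, so its closed-loop time is nil and the definition leaves it without a treatment period.
- Visit schedule: periods last 6 calendar weeks in every arm, not the hours for which the loop ran.
- Secondary outcome: if the period consisted of closed-loop time, the percentage of it spent in closed loop would be 100% by construction.

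**Size of the shift if loop-off hours were dropped from a BiAP arm.** Let c be the fraction of valid CGM time in closed loop, and g the time in range with the loop on minus that with it off.

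- All readings: c × T_on + (1 − c) × T_off
- Closed-loop readings only: T_on
- Difference: (1 − c) × g

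The documents give neither c nor g. With c assumed at 70-90% and g at 8-12 points:

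| c | g = 8 | g = 12 |
|---|---|---|
| 0.90 | 0.10 × 8 = 0.8 | 0.10 × 12 = 1.2 |
| 0.70 | 0.30 × 8 = 2.4 | 0.30 × 12 = 3.6 |

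Against the 12 points used for power: 0.8/12 = 7% and 3.6/12 = 30%. Wider assumptions widen the range: c = 0.95 with g = 6 gives 0.3 points, and c = 0.50 with g = 12 gives 6.0.

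**Between the two BiAP arms.** The shift in the difference is (1 − c₁)g₁ − (1 − c₂)g₂, which is zero when uptime and gap are the same in both arms.

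**The Visit 3 stay.** From 17:00 to 18:00 the next day is 25 h. Six weeks is 42 × 24 = 1008 h, and 25/1008 = 2.5%. Assume the loop was closed throughout the stay and BiAP raises time in range by 8-12 points over control. A control-first participant's control value then rises by 25 × 8/1008 = 0.20 to 25 × 12/1008 = 0.30 points. If a third of participants start with control, the control mean rises by 0.07-0.10. This works against BiAP and is small.

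**The case against.** The strongest reply is that no outcome definition mentions loop status. The treatment-period sentence stands in a background section on route and dosage, directly after the text on 5-minute microboluses, and says nothing about time in range or CGM data. Taken as an outcome rule it would leave control with no data, so it can hardly be the intended one. The 6-week periods and the separate closed-loop outcome both point to calendar time. The Consent text in section 6.0, which keeps participants given alternative treatment in the data analysis, leans the same way, although it covers only changes made by the health care professional.

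This reply stands against several stronger readings:

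- A reader might infer that the protocol holds competing definitions of the primary outcome, one limited to closed-loop time. It does not. The timing phrases in Hypothesis 1 and section 3.0 can be read together, as six weeks of CGM scored at the end-of-period visit, and the second follows the secondary list and may not govern the primary outcome at all.
- A reader might set the shift against the 6-point difference in section 3.0. That figure is for ABC4D versus fixed bolus, where the shift largely cancels.
- A reader might count sensor-failure hours among those lost from BiAP only. They yield no CGM in any arm. Only controller failure and user switching leave valid readings to be dropped.
- A reader might infer a power loss that depends on whether the whole period or its last weeks are scored. The documents give no effect or SD by window, so none can be computed.

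The reply does not supply the missing window. It also leaves in place a definition that fails for one arm and contradicts the schedule.

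**Conclusion.** The point holds as under-specification of the primary outcome beside an inapplicable definition of treatment period. The window and denominator are not stated, and the section 1.0 sentence cannot be reconciled with the control arm, the 6-week periods or the closed-loop secondary outcome as they stand. No bias is shown to be planned. The 0.8-3.6 points are what would follow if the sentence were applied to the BiAP arms while control kept all its hours. They rest wholly on an assumed active fraction and gap, and their direction rests on control being worse with the loop off. The comparison at risk is BiAP against control. The Visit 3 hours are a definite gap in the rule, but of minor size. The plan should be corrected before any outcome data are summarised, because the correction is cheap and the primary comparison depends on it.

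**What to change.** State the primary outcome as the percentage of all available CGM readings within 3.9-10.0 mmol/l over one calendar window per period, defined identically in all three arms and analysed by allocated arm whatever the loop status. Start the window at the actual start of the allocated intervention and end it at the end-of-period visit. In period 1 that start comes after the Visit 3 training stay, for every participant. Periods 2 and 3 begin after a wash-out with no visit scheduled at its end, so the start date and time need recording. Add a minimum amount of CGM data for a period to count, in place of case-by-case judgement.

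Limit the section 1.0 treatment-period sentence to the outcome on percentage of time in closed loop, or reconcile it with the 6-week periods. Report time in range during closed loop only as a supportive analysis.

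The cost is protocol and SAP wording and a recorded start time for each period. The one downside is that the BiAP estimate may look slightly less favourable than a closed-loop-only figure, because loop-off time is counted.

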5.0 Safety

During intercurrent illness, study visits will be postponed as insulin requirements will be altered.

Adverse Event Reporting

Adverse events will be reported to the Health Research Authority (HRA), the sponsor and the Chief Investigator (CI) immediately. Participants will be followed-up after one week following an adverse event and thereafter in the diabetes clinic or any other clinically indicated follow up. A reporting log form will be kept in the TMF.

A "serious adverse event" is one of which:

- a) led to death,
- b) led to serious deterioration in the health of the subject, that earlier resulted in ;
 - 1) a life-threating illness or injury, or
 - 2) a permanent impairment of a body structure or a body function, or
 - 3) in-patient or prolonged hospitalization, or
 - 4) medical or surgical intervention to prevent life-threating illness or injury or permanent impairment to a body structure or body function,
- c) led to foetal distress, foetal death or a congenital abnormality or birth defect.

Summary Reports

In addition to the reporting of individual serious adverse events as detailed above, a summary report of all serious adverse events on a 6 monthly basis will be notified to HRA, sponsor and CI. A table will be reported including the number of serious adverse events, number of participants affected by those events and percentage of the total number or enrolled participants affected by those events.

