6.0 Regulatory Issues

Ethics Approval

The Chief Investigator, [name], has obtained approval from the National Research Ethics Service Committee London-Stanmore. The study must be submitted for Site Specific Assessment (SSA) at each participating NHS Trust. The Chief Investigator will require a copy of the Trust R&D approval letter before accepting participants into the study. The study will be conducted in accordance with the recommendations for physicians involved in research on human participants adopted by the 18th World Medical Assembly, Helsinki 1964 and later revisions.

Consent

Consent to enter the study will be sought from each participant only after a full explanation has been given, an information leaflet offered and time allowed for consideration. Delegated research health care professional will obtain signed participant consent. The right of the participant to refuse to participate without giving reasons will be respected. After the participant has entered the study the health care professional remains free to give alternative treatment to that specified in the protocol at any stage if he/she feels it is in the participant's best interest, but the reasons for doing so should be recorded. In these cases the participants remain within the study for the purposes of follow-up and data analysis. All participants are free to withdraw at any time from the protocol treatment without giving reasons and without prejudicing further treatment.

Confidentiality

The Chief Investigator will preserve the confidentiality of participants taking part in the study and is registered under the Data Protection Act.

Indemnity

Imperial College London holds negligent harm and non-negligent harm insurance policies which apply to this study.

Sponsor

Imperial College London will act as the main Sponsor for this study. Delegated responsibilities will be assigned to the NHS trusts taking part in this study.

Funding

The Wellcome Trust is funding this study.

Audits

The study may be subject to inspection and audit by Imperial College London under their remit as sponsor and other regulatory bodies to ensure adherence to GCP and the NHS Research Governance Framework for Health and Social Care (2nd edition).

Study Management

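### Minor, cheap improvement: a second severe hypoglycaemia or stopping CSII ends study participation as well as use of the allocated system, and no outcome assessment is described at the stop

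*Combined protocol and SAP*

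**What the plan says.** Section 2.0, Subject withdrawal criteria, opens with "Participants will be withdrawn from the study in the case of" and lists four events. Criterion 2 is "Cessation of CSII as usual care for type 1 diabetes". Criterion 3 is "Recurrent (>1 episode) severe hypoglycaemia (defined as needing 3rd party assistance"), with no arm or period specified. The list is followed by "Withdrawal will be immediate and participants will be followed up in the appropriate outpatient diabetes clinic within 4 weeks of withdrawal".

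Section 5.0, Adverse Event Reporting, adds: "Participants will be followed-up after one week following an adverse event and thereafter in the diabetes clinic or any other clinically indicated follow up". This too is clinical follow-up.

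Section 6.0, Consent, deals with a clinician who gives treatment other than that in the protocol: "In these cases the participants remain within the study for the purposes of follow-up and data analysis". It does not mention the withdrawal criteria.

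Section 3.0 lists severe hypoglycaemia, Gold score, quality of life and device acceptability as secondary outcomes and plans three paired comparisons. For missing or spurious data, one option is that "the visit may be removed from the analysis with appropriate justification adjudicated by the Principal Investigator". Section 2.0 describes the trial as open label.

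Visits 4, 5 and 6 each include the Gold score, the questionnaires, an interview and an acceptability form at the end of a six-week period.

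**The concern.** Stopping a device for safety and leaving a trial are different events, and the withdrawal criteria treat them as one. Criteria 2 and 3 are sound reasons to stop the allocated system. They do not require the trial to give up the assessment it already has designed for the end of each period.

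Under criterion 3 the loss depends on an outcome. The missing Gold score and questionnaires would come from participants who have just had a second severe episode, whose hypoglycaemia awareness and treatment satisfaction are of particular interest. Criterion 2 is not itself an outcome, so this argument does not extend to it.

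A second point concerns the primary comparison. When a period is cut short, someone must decide whether its CGM data count. Section 3.0 leaves that decision to the Principal Investigator after the event, and no blinding of it is described. Because the comparisons are paired, the decision changes how many pairs that participant contributes.

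**Working it through.** **The plan's own figure.** The plan gives no withdrawal rate, so there is none to reproduce. Its one related figure is 20 participants for 90% power with a mean of 12 points and SD 9.9. With 9.9 read as the SD of the paired difference and a two-sided paired t test at 0.05/3, 13 participants suffice and 20 give 99.5%. The stated figure is not reproduced on that reading. That is a separate matter, and nothing below depends on it.

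**Inputs.**
- From the protocol: 20 participants; periods and wash-outs of 6 + 2 + 6 + 2 + 6 = 22 weeks from Visit 3 to Visit 6; exit at the second severe episode; three comparisons, so 60 planned pairs.
- Assumed: a Poisson process with the same constant rate r for everyone, with r = 0.1, 0.5 or 1.0 episodes per person-year. The top value is an upper end, because section 2.0 excludes people with more than one severe episode in the preceding year and those with "Impaired awareness of hypoglycaemia (Gold score >4").

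**Expected exits on criterion 3.** λ = 22r/52; p = 1 − exp(−λ)(1 + λ).

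| | r = 0.1 | r = 0.5 | r = 1.0 |
|---|---|---|---|
| λ | 0.042 | 0.212 | 0.423 |
| p | 0.0009 | 0.0195 | 0.0678 |
| Expected exits, 20p | 0.02 | 0.39 | 1.36 |
| At least one exit, 1 − (1 − p)^20 | 1.7% | 32.5% | 75.5% |
| Three or more exits (binomial) | <0.001% | 0.7% | 15% |

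Stops of CSII would come on top, at a rate that the documents do not give.

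**End-of-period assessments lost.** The time of the second episode has distribution function F(w) = 1 − exp(−rw/52)(1 + rw/52), with w in weeks. At r = 0.5 the shares falling in period 1, wash-out 1, period 2, wash-out 2 and period 3 are 8.2%, 6.2%, 28.1%, 12.3% and 45.1%. An exit in a wash-out interrupts no period. The share inside a period is 8.2 + 28.1 + 45.1 = 81.4%, so the expected number of lost assessments is 0.39 × 0.814 = 0.32. The same steps give about 0.01 at r = 0.1 and 1.10 at r = 1.0.

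**Usable pairs.** For a stop in those five segments, a participant supplies 0/0/0/1/1 pairs if the interrupted period is left out and 0/0/1/1/3 if it is kept.

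| | r = 0.1 | r = 0.5 | r = 1.0 |
|---|---|---|---|
| Mean pairs per exit, left out | 0.59 | 0.57 | 0.55 |
| Mean pairs per exit, kept | 1.80 | 1.76 | 1.70 |
| Expected difference over 60 pairs, 20p × (kept − left out) | 0.02 | 0.46 | 1.56 |

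This is a best case, since it counts a period stopped on its second day as usable. If at least two weeks of data are required (an assumption), the difference falls to 0.32 at r = 0.5 and 1.09 at r = 1.0. With four weeks it falls to 0.17 and 0.56. If the trial would have kept the data anyway, it is zero.

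**Precision.** The 95% half-width is t(0.975, n − 1) × 9.9/√n. For n = 20 it is 2.093 × 9.9/√20 = 4.63 points; for n = 19 it is 2.101 × 9.9/√19 = 4.77 points.

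**Telephone follow-up to the planned Visit 6 date.** Expected further severe episodes are 20 × (r/52) × ∫(22 − w)f(w)dw over 0 to 22, with f the density of F. The results are 0.0002, 0.03 and 0.2.

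**The case against.** Much of the case on the other side stands.

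- **A reader might infer that data from before the stop are thrown away.** No text says so. Section 1.0 (system architecture) has data sent to the research team, and section 4.0 has glucose and dose data stored on the BiAP device, with CGM visible to the team. At least in the BiAP arms, the primary-outcome data to the stop are already captured. The uncertainty about their use comes from the general missing-data rule in section 3.0, not from the withdrawal criteria.
- **A reader might infer that sections 2.0 and 6.0 contradict each other.** A list of mandatory exits can stand beside a general rule for discretionary changes of treatment. They pull apart only where a clinician moves a participant to other treatment because of a second severe episode or because CSII has ended. That is a tension to settle, not a contradiction.
- **The rates are unsourced.** The only evidence in the documents (section 1.0, Potential risks and benefits) is that earlier BiAP and ABC4D studies had no severe excursions. Those studies were short or small, but they favour the low scenario.
- **Keeping truncated periods is not clearly better.** Hypothesis 1 concerns six weeks of use, and ABC4D learns from accumulated cases. A short ABC4D period over-represents use before adaptation.
- **Ending exposure after a second severe episode is a defensible safety rule.** It should stay.

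None of this answers the remaining point: the end-of-period assessment is not described for a participant who exits part-way through a period.

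**Conclusion.** The point holds as a minor one. The text makes criteria 2 and 3 exits from the study and describes only clinical follow-up, so the Gold score, questionnaires and acceptability form for the interrupted period are not collected. Under criterion 3, that missingness is related to a listed outcome.

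Exits are probably 0 or 1 of 20, and slightly more are expected only at the upper-end rate. This rests on assumed rates, a common Poisson process and no allowance for CSII stops. The pair differences are upper limits on what a rule about interrupted periods could gain, and one lost participant widens a 95% interval by 0.14 points on each side (4.77 − 4.63).

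A reader might go further and infer bias for or against one arm. The documents do not support that: they give no event rates by arm, and the direction is unknown. They also do not show that any conclusion of the trial would change.

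**What to change.** 1. Make criteria 2 and 3 reasons to stop the allocated system at once and start no further arm, with the participant staying in the study unless consent is withdrawn. Criteria 1 and 4 remain full withdrawal. Refer to the Consent text in section 6.0 so that the two sections agree.
2. At the stop, carry out the end-of-period assessment: BiAP/CGM and pump download, Gold score, questionnaires and acceptability form.
3. State in section 3.0 that data from before the stop are retained under the arm in use. Fix in advance the minimum number of CGM days for an interrupted period to count in the paired primary comparison, and report results with and without interrupted periods.
4. Report stops by arm, period and reason.
5. Telephone recording of severe hypoglycaemia and ketoacidosis to the planned Visit 6 date is optional and adds little. Off-system events would have to be shown separately.

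The cost is protocol wording, a line in the consent form and one unscheduled assessment for each affected participant, possibly none. The change does not recover arms not yet reached, and an interrupted ABC4D period will still reflect mostly early use.
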